### Univariate analysis

Similarly, the secondary endpoint will be measured as a count variable. The hypothesis will be tested using a generalized linear mixed model (GLMM) with a log link function and Poisson or negative binomial distribution. The model uses the secondary endpoint as the dependent variable, and the intervention effect (intervention vs. control) as the independent variable or the fixed

effect with site as a random effect. For all different types of unscheduled healthcare visits and the sum of all healthcare visits, we will calculate the point estimates (i.e., average hospitalizations, average ER visits, average unscheduled healthcare visits, and the average of all visits) and their respective 95% CIs for each intervention group and for the difference in average visits between the intervention groups. We will also report the p-value of the difference in point estimates between intervention groups.

#### Multivariable analysis

We will assess the impact of intervention effect on each type of unscheduled healthcare visit using a multivariable GLMM controlling for potential confounders. For all types of unscheduled healthcare visits and the sum of all visits, we will calculate adjusted point estimates (i.e., average hospitalizations, average ER visits, average unscheduled healthcare visits, or the average of total visits) and respective adjusted 95% CIs for each intervention group and for the difference in average unscheduled healthcare visits between the intervention groups. We will report the adjusted p-value of the difference in point estimates between intervention groups.

#### Secondary Endpoint 2: QOL score

We will test the following null hypothesis:

Null hypothesis: Child QOL will not differ in families that receive the HEPA intervention compared to controls.

vs

Alternative hypothesis: Child QOL will be higher in families that receive the HEPA intervention compared to controls.

Total QOL score or Total Scale Score (TSS), is measured by the PedsQL™ Pediatric Quality of Life Inventory Infants Scales questionnaire at the end of the intervention period. Total QOL score will be calculated as the sum of all the items on the scales divided by the number of items answered. Caregivers with children at age 1-12 months will use a 36-item PedsQL, and those with children at age 13-24 months will use a 45-item PedsQL. In each item, a score is assigned at 100 if the answer is “never a problem”; 75 if the answer is “almost never a problem”; 50 if the answer is “sometimes a problem”, 25 if the answer is “often a problem”; and 0 if the answer is “almost always a problem” respectively (Varni et al., 2011).

**Univariate analysis:**

The total QOL score will be measured as a continuous variable. The hypothesis will be tested using a mixed effect model after accounting for within-cluster correlation. The model uses the QOL score as the dependent variable, and the intervention effect (intervention vs. control) as the independent variable or the fixed effect with site as a random effect. We will calculate the point estimates (i.e., average QOL score) and their respective 95% CIs for each intervention group and for the difference in average QOL score between the intervention groups. Additionally, we will present the p-value of the difference in point estimates between intervention groups.

**Multivariable analysis:**

Similarly, we will adjust for confounders for the impact of intervention effect on the QOL score using a multivariable mixed effect model. We will calculate adjusted point estimates (i.e., average QOL score) and respective adjusted 95% CIs for each intervention group and for the difference in average QOL score between the intervention groups. We will report the adjusted p-value of the difference in point estimates between intervention groups.

**Secondary Endpoint 3: PM2.5**

Data related to PM2.5 will be generated from two PurpleAir monitors installed in each participating home. Weekly average PM2.5 levels as measured in each room separately and by the average of the two in-home PurpleAir monitors over 24 weeks and scaled to the unit of  $\mu\text{g}/\text{m}^3$  per week. Log transformations of the PM2.5 data will be considered if data are skewed. We will compare the weekly average PM2.5 levels in each room separately and the average of the two monitors between intervention and control groups using the same unadjusted and adjusted mixed-effect models as described for the secondary endpoint QOL score.

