6 STUDY INTERVENTION

6.1 STUDY INTERVENTIONS ADMINISTRATION

6.1.1 STUDY INTERVENTION DESCRIPTION

The 24-week intervention period captures the period of highest respiratory burden post-bronchiolitis.

Use of the HEPA units (experimental) or inactive (control) units takes place for 24 weeks beginning after a pre-intervention period approximately 2 weeks in duration (methods to be described in the MOP).

Since previous related work using a pre-/post-design has shown substantial variability in PM_{2.5} concentrations even in relatively small geographic areas, we will collect baseline PM_{2.5} to control for this potentially important source of variability in homes. For example, in a study in homes with wood stoves in the western U.S., baseline median PM_{2.5} was 17, 41, and 16 µg/m³ in filter, wood stove change out and placebo arms, respectively.⁶⁹ Preliminary results from an ongoing RCT (NCT02240069) have shown a similar pattern with median baseline PM_{2.5} ranging from 23 to 41 to 30 µg/m³ in homes assigned to different intervention arms.⁹⁶ Note we will not exclude homes based on baseline PM_{2.5} measurements because even at low levels (i.e., below U.S. National Ambient Air Quality Standards), PM_{2.5} has demonstrated adverse health effects.⁹⁷

The rationale for placing the HEPA unit in the child's sleep space is that the child will typically spend a continuous number of hours daily in this space. The rationale for a second HEPA unit in a common area of the home is to maximize exposure to the intervention.

Intervention for both experimental and control conditions:

- Use of the HEPA units (experimental) or control units takes place from weeks 3-26 (approximately) after hospital discharge to home.
- A coordinator or other qualified research team member will contact the family via video or phone to prompt them to begin using the HEPA or control units. The research team member will confirm proper installation and that the two units are functioning and provide information on the lights (e.g., sensor light) on the units.
- Both the HEPA and carbon filters will be removed from the control units, and interior contents of the unit will be masked with black cardstock or similar. The door on the unit will be taped closed to make it difficult to open the units.

Title: *The BREATHE Study: Bronchiolitis Recovery and the Use of High Efficiency Particulate Air (HEPA) Filters*

Sponsor: ISCPTN DCOC

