8 STUDY ASSESSMENTS AND PROCEDURES

8.1 EFFICACY ASSESSMENTS

Collection of participant characteristics and risk factors for recurrent wheeze:

History will be obtained at the start and end of the study to ensure randomization provides similar characteristics of the intervention and control groups. If there is an imbalance between arms, we will control for these factors in the primary analysis.

Table 4. Participant characteristics and risk factors for recurrent wheeze

Collect information at baseline or intervention start (by parental report unless otherwise indicated)

• Age (in months) at initial hospitalization for bronchiolitis (medical record review)• Gestational age at birth (parental report or medical record review)• Sex/gender (parental report or medical record review)• Race/ethnicity (parental report or medical record review)• Parental education• Rural/Urban (RUCA code) based on residential address• Viral test results (first hospital admission for bronchiolitis) if available per standard of care testing (medical record review)• Season of hospitalization for bronchiolitis (medical record review)• Highest level of respiratory support during bronchiolitis admission (medical record review)• History of previous wheezing with illness• Family history of asthma• Wood stove use in the home (and whether this is the primary heat source)

- Central air conditioning in the home
- Type of cooking stove in the home
- Presence of hood above cooking stove in home
- Use of hood while cooking
- Risk of higher frequency of viral exposures
 - Daycare attendance
 - Number of children in home
 - Number of children in home in daycare or school
 - Household crowding
- Presence of plumbed (running) water
- Furry pets in the home
- Baseline weekly average PM_{2.5} home measurements (Purple Air Monitor data report)
- Atopic dermatitis
- Chronic use of asthma medications preceding bronchiolitis hospitalization
- Use of asthma medications with illness preceding bronchiolitis hospitalization -
- Received systemic steroid during hospitalization for bronchiolitis (medical record review)
- Square footage of rooms containing HEPA units (during intervention set-up)
- RSV vaccination/preventive treatment history (by report from family or medical record review)

Collect information at approximately 26 weeks (end of 24-week intervention period) by parental report unless otherwise indicated

- Smokers who live in the home

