9.4 STATISTICAL ANALYSES

9.4.1 GENERAL APPROACH

- **Descriptive Statistics:** All numerical variables will be summarized using mean \pm standard deviation and median (minimum, maximum). All categorical variables will be summarized using frequency (in %).
- **Inference tests:** All proposed statistical tests are two-sided. A p-value <0.05 is considered statistically significant.
- **Covariates:** Covariates will be compared between groups (intervention vs. control) using two sample t-tests, or Wilcoxon rank sum tests if they are continuous variables, and Chi-square tests or Fisher's exact tests if they are categorical variables. Each of the continuous covariate variables will be assessed of its correlation to the primary endpoint, or each of the secondary endpoints using a Pearson's correlation coefficient or a Spearman's correlation coefficient. Similarly, each of the categorical covariate variables will be assessed of its association to the primary endpoint, or each of the secondary endpoints using an ANOVA model, or a Kruskal-Wallis test. A covariate showing a significant association to intervention, a significant correlation or association to the primary (or secondary) endpoint will be considered as the adjusting (controlling) covariate and will be added as adjusting independent variable in the statistical models proposed for primary and secondary analyses.
- **Model assumptions:** Primary and secondary endpoints will be inspected of normal distribution assumptions using the histogram plots. If the variable is noticeably right (or seldomly left) skewed, then a transformation variable will be used in the parametric models to ensure the assumption of normality is met. As an alternative approach, a generalized linear model will be proposed to the variable using a distribution assumption fitting the data properly.

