## 6.5. Data Summary and Visualization

All numerical variables will be summarized using mean  $\pm$  standard deviation and median (minimum, maximum). All categorical variables will be summarized using frequency (%). The variables will be summarized using descriptive statistics overall and stratified by intervention groups (HEPA filtration versus control) as well as by sites. The variables will be compared between groups (HEPA filtration vs. control) using two sample t-tests; or Wilcoxon rank sum tests if they are numerical variables, and Chi-square tests or Fisher's exact tests if they are categorical variables. The choice of a t-test or a Wilcoxon rank sum test will depend on the empirical distribution of the tested numerical variable. The choice of a Chi-square test or a Fisher's exact test will depend on the sample size used in the test.

Under the study design of stratified randomization, it is unlikely to expect any significant association between baseline characteristics and the intervention effect. However, some of the

baseline characteristics could be associated with the endpoints. For a candidate covariate used in multivariate analyses, its correlation to the primary endpoint, or a secondary endpoint will be assessed using a Pearson's correlation coefficient or a Spearman's correlation coefficient when it is a numerical variable. When the covariate is categorical, its association to the primary endpoint, or each of the secondary endpoints will be assessed using an ANOVA model, or a Kruskal-Wallis test. A variable that is associated with the intervention and primary endpoint and secondary endpoints or the association is mentioned in the previous literature will be considered as the adjusting (controlling) covariate and will be added as adjusting independent variable in the statistical models proposed for primary and secondary analyses.

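### Baseline PM2.5 is collected to control for differences between homes, but no PM2.5 model names it as a covariate and neither the unadjusted nor the adjusted model is named as the main one

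*SAP*

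**What the plan says.** **Purpose.** Protocol 6.1.1 explains that PM2.5 varies widely even within small areas and that baseline is measured "to control for this potentially important source of variability in homes". It cites baseline medians of 17, 41 and 16 µg/m³ across the arms of an earlier wood-stove study. Protocol 8.1, Table 4, lists weekly average baseline PM2.5 "home measurements (Purple Air Monitor data report") among the participant characteristics.

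**Models.** Protocol 9.4.3 gives the PM2.5 model as arm (fixed) and site (random). SAP 6.6.2 compares the arms for each room and for the two-monitor average, "using the same unadjusted and adjusted mixed-effect models as described for the secondary endpoint QOL score". The QOL outcome comes from the "Infants Scales questionnaire at the end of the intervention period". Its unadjusted model is arm plus random site; its adjusted model adds confounders that are not named.

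**Other uses of baseline PM2.5 in the SAP.** Table 2 (baseline characteristics and covariates) does not list it. SAP 6.6.3 uses it descriptively, by demographic, environmental and medical factors.

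**Covariate rules.**
- Protocol 8.1: "If there is an imbalance between arms, we will control for these factors in the primary analysis".
- Protocol 9.4.1: "A covariate showing a significant association to intervention, a significant correlation or association to the primary (or secondary) endpoint" qualifies for adjustment.
- SAP 6.5: "A variable that is associated with the intervention and primary endpoint and secondary endpoints or the association is mentioned in the previous literature" qualifies for adjustment. The same section remarks: "Under the study design of stratified randomization, it is unlikely to expect any significant association" between baseline characteristics and the intervention.

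**The concern.** The protocol gives a reason for collecting baseline PM2.5, and the analysis plan does not carry that reason into a model. Borrowing the QOL models is the likely cause: QOL has no baseline, so its model has no place for one, whereas PM2.5 has up to two weeks of pre-intervention data from the same monitors.

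PM2.5 is the endpoint meant to show that the filters lowered exposure, so the size and precision of the reduction matter as well as its p-value. Two things are at stake. The unadjusted estimate forgoes precision that is already paid for. And whether baseline enters the adjusted estimate, and which of the two estimates is the PM2.5 result, can be decided after the data are seen. Three outcomes (two rooms and their average) times two models gives six PM2.5 results, with none named as the main one. SAP 3.9 plans no blinded data review at which this could be settled.

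**Working it through.** **1. The plan's own figure.** The only power statement concerns symptom-free days: 98 per arm, difference 20, SD 43, two-sided 0.05. It reproduces: 0.902 by the normal approximation and 0.900 by the t-test, against the stated 90%. None is given for PM2.5. It supplies only the sample size used below, 196 homes.

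**2. Where baseline PM2.5 could enter.**

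| Place | Is baseline PM2.5 in? |
|---|---|
| Protocol 9.4.3 PM2.5 model | No |
| SAP unadjusted model | No, by construction |
| SAP adjusted model | Not named; depends on the covariate rule |
| SAP Table 2 | No |
| SAP 6.6.3 | Yes, descriptively only |
| Protocol 8.1 imbalance clause | Only if imbalanced, and written for the primary analysis |

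**3. Would the covariate rules admit it?** Under Protocol 9.4.1, correlation with the endpoint is enough. The expected t statistic is r × √(194 / (1 − r²)), with no arm effect:
- r = 0.3: 0.3 × √(194/0.91) = 4.4
- r = 0.5: 0.5 × √(194/0.75) = 8.0
- r = 0.7: 0.7 × √(194/0.51) = 13.7

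All are far above 1.97, so the protocol rule would almost surely admit it. SAP 6.5 asks for association with the intervention as well as the endpoints, which randomisation makes unlikely, or else for support in the literature. In practice the literature route decides, and that is a judgement. Both routes probably lead to entry; neither guarantees it.

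**4. What omission costs relative to the unadjusted model.** The baseline-to-outcome correlation r is not in the documents, so a range is assumed. Variance ratio = 1 − r²; standard-error ratio = √(1 − r²); equivalent homes = 196 / (1 − r²).

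| Assumed r | Variance ratio | Variance reduction | SE ratio | Interval narrower by | Equivalent homes |
|---|---|---|---|---|---|
| 0.3 | 0.91 | 9% | 0.954 | about 5% | 215 |
| 0.5 | 0.75 | 25% | 0.866 | about 13% | 261 |
| 0.7 | 0.51 | 49% | 0.714 | about 29% | 384 |

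A simulation (196 homes, 17 sites, allocation about 1:1 within site, no arm effect, one outcome per home, site as fixed effects in place of the random effect, 4,000 runs per r) gave SE ratios of 0.956, 0.869 and 0.717. Rejection rates were 5.0%, 5.0% and 4.9% unadjusted, and 5.2%, 5.0% and 4.8% adjusted. Omission therefore costs precision, not validity.

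**5. Which end of the range?** Baseline covers at most 14 days (Schedule of Activities, footnote 4), ideally at least four (Protocol 8.1), against an outcome over 24 weeks. Protocol 4.2 itself mentions variation with heating season. Both could pull r towards the low end.

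**The case against.** The strongest reply is that the existing text already deals with this. The SAP says it is to be read together with the protocol, the protocol states the purpose of the baseline measurement and cites earlier studies, and an adjusted PM2.5 model is planned. Once baseline enters that model, the gain from naming it is about zero. This stands, and it limits the size of the point. What remains is that entry is not guaranteed, that the unadjusted model cannot contain it, and that neither model is designated as the main one.

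It is also fair that adjustment is not entirely free. SAP 6.6.3 separates out homes with at least four days of baseline data, so some are expected to have fewer. Making baseline mandatory without a rule for such homes could drop them from the comparison.

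A reader might go further and infer that the PM2.5 test has an inflated false-positive rate, because the SAP speaks of comparing weekly averages while the borrowed model has no home-level term. If 24 weekly rows per home were fitted with site as the only random effect, the design effect would be 1 + 23 × ICC. At assumed within-home correlations of 0.1 to 0.7 that is 3.3 to 17.1, so standard errors would be too small by a factor of 1.8 to 4.1 (the square roots). The documents do not support that as a finding. The QOL model applied literally takes one value per home, which is valid. Protocol 8.1 has the central site deliver final summary PM2.5 metrics, and the referenced model is described as allowing for clustering. The unit is unstated; no error is planned.

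**Conclusion.** The point holds as a matter of precision and pre-specification. Baseline PM2.5 is collected for adjustment and is not named in any PM2.5 model; its use and the choice of main model are left open.

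Against the unadjusted model, the forgone variance reduction is 9% to 49% for assumed r of 0.3 to 0.7, quite possibly nearer the low end. Against an adjusted model that admits baseline anyway, it is about nil.

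A reader might infer that the PM2.5 comparison is biased, or that baseline is barred from the adjusted model. Neither follows: randomisation protects the comparison, and both covariate rules leave a route in. The primary symptom-free-day test is unaffected. Near the 50% reduction in PM2.5 that the protocol cites for portable air cleaners, the significance conclusion for this endpoint would probably not change.

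**What to change.** In SAP 6.6.2, Secondary Endpoint 3:

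1. Pre-specify baseline PM2.5 as a covariate, for the same room (or the same average) as the outcome, and logged if the outcome is logged.
2. Name this baseline-adjusted model as the main PM2.5 analysis.
3. State how homes without a usable baseline stay in the analysis, for example by a missing-baseline indicator or by imputing baseline.
4. As a minor clarification in the same edit, state that the outcome is one 24-week mean per home. If weekly rows are intended, add a home-level random effect and a week term.

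The cost is a few lines of SAP text and model code. The data are already collected and trial conduct does not change. The one small burden is the rule in item 3.

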**6.6.3. Additional Analysis**

Descriptive analysis will be conducted to compare baseline pre-intervention PM2.5 levels by demographics, environmental factors, and medical history for the common room and sleep space, respectively. The average or median pre-intervention hourly PM2.5 levels will be calculated for 1) all participants who have available PM2.5 data; and 2) participants who have at least four days of pre-intervention PM2.5 data. The demographics and baseline variables will include the infant's race, infant's ethnicity, rurality, parental education, the season of hospitalization, wood stove

use, use of central AC, type of cooking stove, presence of hood, use of hood while cooking, whether the participant infant attends daycare, number of other children in the home, number of other children in home attend daycare or school, any furry pets in the home, previous history of wheezing with colds or other illnesses, history of asthma, chronic asthma medication used before hospitalization, asthma medication with other breathing illnesses, and the highest level of respiratory support.

## **6.7. Safety Analysis**

Any AE related to the study groups specific to child participants will be documented and summarized as overall and by study groups using descriptive statistics. Safety analysis and reports will be made as specified in the Data Safety and Monitoring Plan (DSMP).

### **6.7.1 Adverse Events**

Adverse events constitute any untoward or unfavorable occurrence in a research participant associated with the involvement in the research that may or may not be related to their participation in research. The adverse events will be collected and coded in accordance with the guidelines specified in MedDRA/CTCAE.

Unexpected adverse events refer to adverse events occurring in participants when they deviate from the following guidelines:

- Risks outlined in study-related documents (e.g. approved research protocol, investigator brochure)
- Anticipated course of any pre-existing health conditions, diseases, or disorders in the affected individuals, considering their specific risk factors.

The analysis and listing of adverse events will be done for safety population. The summary statistics will be presented (if applicable) by organ class, study groups, study phase, severity, expectedness, and relatedness to the study intervention. The severity for adverse events will be presented as per the guidelines specified by “The Common Terminology Criteria for Adverse Events” (CTCAE) developed by the US National Cancer Institute (NCI).

Adverse events will be analyzed and listed as per the guidelines listed below:

1. If a participant experiences same AE multiple times during the study, the patient will be counted only once in the number of participants experiencing the event.

2. If a patient experiences same AE multiple times but with different severities during the study, the worst or most intense event will be counted.
3. If there are adverse events that are not coded, the summary table will use the exact description as reported in the database. The statistician may consult with the study investigator for further information to resolve this (i.e. whether it can be reassigned to one of the existing coding). Any decisions made in this regard will be documented (either by including as a footnote or as an appendix).

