8.3 ADVERSE EVENTS AND SERIOUS ADVERSE EVENTS

8.3.1 DEFINITION OF ADVERSE EVENTS (AE)

An AE is any untoward or unfavorable medical occurrence in a human subject, including any abnormal sign, symptom, or disease, temporally associated with the volunteer's participation in research, whether or not it is considered related to the research intervention. Stable chronic conditions that are present prior to enrollment and do not worsen are not considered AEs and will be accounted for in the subject's medical history. Exacerbation or worsening of pre-existing conditions are defined as AEs. Each AE will be classified by the investigator as serious (SAE) or nonserious. All AEs will be evaluated for severity, action taken, seriousness, outcome, and relationship to the study intervention. Information on protocol-specific AEs, severe AEs, and SAEs will be collected from participant reports and via phone calls, as well as review of weekly surveys. Protocol-specific AEs, severe AEs and SAEs will be collected for the duration of the study. We will only record and track severe AEs; SAEs; and AEs associated with the study intervention and/or study equipment.

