8.3.3 CLASSIFICATION OF AN ADVERSE EVENT

8.3.3.1 SEVERITY OF EVENT

For AEs, the following guidelines will be used to describe severity.

- **Mild** – Events require minimal or no treatment and do not interfere with the participant's daily activities.
- **Moderate** – Events result in a low level of inconvenience or concern with the therapeutic measures. Moderate events may cause some interference with functioning.
- **Severe** – Events interrupt a participant's usual daily activity and may require systemic drug therapy or other treatment. Severe events are usually potentially life-threatening or incapacitating. Of note, the term "severe" does not necessarily equate to "serious".

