8.3.4 TIME PERIOD AND FREQUENCY FOR EVENT ASSESSMENT AND FOLLOW-UP

All potentially related, severe AEs, and SAEs will be recorded on the appropriate CRF. Information to be collected includes event description, approximate date of onset, clinician's assessment of severity, relationship to study intervention (assessed by site investigator or qualified clinician designee), and date of the resolution/stabilization of the event. SAEs occurring while on the study must be documented appropriately regardless of relationship; and must be followed until one of the following criteria is met: study completion, resolution, the condition stabilizes, the event is otherwise explained or is judged by the site investigator or qualified clinician designee to be no longer clinically significant, or the participant is lost to follow up.

Any medical condition that is present at the time that the participant is screened will be considered as baseline and not reported as an AE. However, at the onset of the intervention and anytime during the study if the study participant's condition deteriorates and meets the definition of severe AE, SAE, or is possibly related to the study intervention, it will

Title: *The BREATHE Study: Bronchiolitis Recovery and the Use of High Efficiency Particulate Air (HEPA) Filters*

Sponsor: ISCPTN DCOC

be recorded as an AE. Changes in the severity of an AE will be documented to allow an assessment of the duration of the event at each level of severity to be performed. AEs characterized as intermittent require documentation of onset and duration of each individual episode.

The site investigator or qualified designee will record all potentially related, severe AEs, and SAEs with start dates occurring any time after informed consent is obtained until 30 days after the last day of study participation. At each study visit or interval phone call, the investigator will inquire about the occurrence of potentially related, severe AEs, and SAEs since the last visit. Events will be followed for outcome information until resolution or stabilization.

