### **6.7.2 Deaths, Serious Adverse Events, and other Significant Adverse Events**

Serious adverse events refer to the adverse events that meet at least one of the following criteria:

- Lead to death
- Considered life threatening (putting participants in immediate risk of death)
- Necessitate inpatient hospitalization or prolongation (if already hospitalized)
- Result in congenital anomaly or birth defect
- Result in persistent or significant disability/incapacity
- Require medical or surgical intervention to prevent outcomes listed in the above definition of SAE
- Cause significant psychological, social, economic, or legal harm to participants or others

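### The SAP's CTCAE severity scale and SAE criteria differ from the protocol's, so the severity and SAE tables would not match the data as classified under the protocol

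*SAP*

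**What the plan says.** **Severity.** Protocol 8.3.3.1 introduces its three-level scale with "For AEs, the following guidelines will be used to describe severity" and defines mild, moderate and severe in its own words. On the top level it says: "Severe events are usually potentially life-threatening or incapacitating". The protocol does not mention CTCAE. SAP 6.7.1 states: "The adverse events will be collected and coded in accordance with the guidelines specified in MedDRA/CTCAE". Later in the same section it says "The severity for adverse events will be presented as per the guidelines specified by" CTCAE. It gives no CTCAE version, list of grades or mapping from the protocol scale.

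**What is recorded.** Protocol 8.3.1 limits capture: "We will only record and track severe AEs; SAEs; and AEs associated with the study intervention and/or study equipment". Protocol 8.3.4 requires a clinician's severity assessment for each recorded event, and adds: "Changes in the severity of an AE will be documented to allow an assessment of the duration of the event".

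**Serious events.** Protocol 8.3.2 has five criteria and SAP 6.7.2 has seven. One that appears only in the SAP is "Cause significant psychological, social, economic, or legal harm to participants or others".

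**Tables.** SAP 6.7.1 plans the following: "The summary statistics will be presented (if applicable) by organ class, study groups, study phase, severity, expectedness, and relatedness to the study intervention".

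**The concern.** A SAP should tabulate safety data on the definitions under which they were collected. Here the two documents state different rules for two classifications, severity and seriousness.

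Severity is more than a label in this trial, because the protocol's *severe* category also acts as the entry threshold for unrelated, non-serious events. A table headed CTCAE would describe events selected by another scale. If sites recorded only the protocol grade, producing CTCAE grades would mean regrading afterwards, and events that fell below the protocol threshold would not be there to regrade.

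For serious events, the count in the final report would depend on which document the programmer followed. If the choice is left until analysis, it may be made with results by group in view and without a record of why.

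**Working it through.** No formula applies, since the point involves no sample size, error rate or event count. The check is a comparison of the two texts.

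**Step 1: severity scales.** The protocol has three levels. Its top level takes in potentially life-threatening events, and no separate level exists for life-threatening or fatal ones. The SAP names CTCAE without listing its levels. The documents contain no rule that turns one into the other.

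**Step 2: how the protocol grade filters the data.** Under protocol 8.3.1 an event is recorded if it is severe, or serious, or associated with the intervention or equipment.

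- Related or serious events are recorded at any grade.
- Unrelated, non-serious events are recorded only if graded severe on the protocol scale.

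Mild and moderate rows can therefore hold only related or serious events. What the table contains is fixed by the protocol scale, whatever scale is used to present it.

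**Step 3: SAE criteria side by side (paraphrased).**

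| Criterion | Protocol 8.3.2 | SAP 6.7.2 |
|---|---|---|
| Death | yes | yes |
| Life-threatening event | yes | yes |
| Hospital admission or longer stay | yes | yes |
| Lasting or significant incapacity | yes | yes |
| Other important medical event | by medical judgment; *may* jeopardize the child and *may* need intervention | only if intervention is *required* |
| Congenital anomaly | no | yes |
| Psychological, social, economic or legal harm, to participants or others | no | yes |

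Protocol: 4 shared + 1 = 5. SAP: 4 shared + 1 narrower + 2 added = 7.

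**Step 4: events that would be classified differently.**

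- An event that the investigator judges might jeopardize the child, but that did not require intervention, can be serious under the protocol and not under the SAP.
- A confidentiality breach causing social harm would be serious under the SAP. Protocol 8.4.1 places psychological, economic and social harm in the definition of unanticipated problems, and 8.4.2 gives a confidentiality breach as an example that is neither an AE nor an SAE. The SAP's AE definition in 6.7.1 drops the protocol's restriction to medical occurrences, so it would not exclude such a case.
- Congenital anomaly should make almost no difference. Participants are already born, and protocol 8.3.4 treats conditions present at screening as baseline.

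**Step 5: is the difference reconciled anywhere?** SAP section 7, where departures from the protocol's statistical approaches are to be justified, holds only its instruction. The SAP revision table is empty. Protocol 9.4.4 asks for descriptive summaries and does not adopt CTCAE.

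**The case against.** The strongest reply is that the SAP says events are *collected*, not just presented, under MedDRA/CTCAE. SAP section 1 says it must be read with the data collection forms, and SAP 6.7 sends safety reporting to the Data Safety and Monitoring Plan. Neither the forms nor that plan is available here, and either could hold a CTCAE grade or a mapping. This stands. A reader might infer that the planned safety tables cannot be built, and the documents do not support that. They show two conflicting rules, not that CTCAE grades are absent from the database. Breakdowns by organ class, group, phase and relatedness need no severity scale, and the SAP's rule of counting the worst severity works on three ordered levels.

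On serious events, a reader might infer that the SAP list is simply wider. It is different: broader in two places and narrower in one. The four main criteria agree, so most SAE counts should match, and the non-medical harms named in protocol 8.4.1 are still captured there as unanticipated problems.

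A reader might also take the adverse-event tables to be the trial's only safety comparison. They are not. SAP 6.7.5 summarizes weeks of high PM2.5 by group, and hospitalizations and emergency or urgent care visits are compared between arms as Secondary Endpoint 1. Nor are the retained records incomplete: protocol 8.3.4 requires a description, onset, severity, relationship and resolution date for each. The restriction lies in which events are recorded.

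**Conclusion.** The inconsistency is real and unreconciled in the documents, but minor. Two classifications are affected: severity, where the SAP names a scale the protocol does not use, and seriousness, where three of the SAP's seven criteria differ from the protocol's list (two added, one narrowed). The severity and SAE tables would not match the data as classified under the protocol. The other adverse-event tables and all efficacy analyses are unaffected.

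The number of events that would move between categories cannot be derived from the documents. It is likely to be small for serious events, given the four shared criteria and a trial the protocol describes as minimal risk. The conclusion on severity assumes that sites grade as protocol 8.3.3.1 instructs. If the data collection form also holds a CTCAE grade, the severity table has a source, but the documents still disagree and the recording threshold still follows the protocol scale.

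**What to change.** Check the data collection form and the Data Safety and Monitoring Plan first, then:

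1. In SAP 6.7.1, tabulate severity on the protocol 8.3.3.1 scale. Remove CTCAE from both the collection sentence and the severity sentence, and keep MedDRA for coding terms.
2. If the form does capture CTCAE grades, state that in both documents instead, with the version and a crosswalk to the protocol scale, and say which scale decides what is recorded.
3. In SAP 6.7.2, count serious events by the protocol 8.3.2 criteria, and report non-medical harms separately as unanticipated problems.
4. Enter the reconciliation in SAP section 7 before the final analysis.

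Items 1, 3 and 4 cost SAP wording only, with no new data collection. Item 2 would also need a protocol wording change.
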